## 5. STAGE 2 SELECTION OF STUDY POPULATION

### 5.1 Study Population

#### 5.1.1. Inclusion Criteria

This Phase 2 study will enroll up to 111 subjects with MF, 27 in Stage 1, and up to an additional 84 subjects in Stage 2

Each subject must meet all of the following inclusion criteria to be enrolled in the study:

1. Subjects must be  $\geq 18$  years of age at the time of signing the Informed Consent Form (ICF);
2. Subjects must voluntarily sign an ICF;
3. Subjects must have a pathologically confirmed diagnosis of PMF as per the WHO diagnostic criteria (see [APPENDIX C](#)) or post ET/PV MF;
4. At least Grade 2 marrow fibrosis according to the WHO Grading of Bone Marrow Fibrosis ([APPENDIX D](#));
5. Intermediate -1, intermediate -2, or high risk disease according to the IWG-MRT Dynamic International Prognostic Scoring System (see [APPENDIX E](#));
6. A bone marrow biopsy must be performed within four weeks prior to Cycle 1 Day 1 treatment to establish the baseline fibrosis score;
7. Subjects must not be candidates for ruxolitinib based on EITHER:
  - a. Platelet count  $< 50 \times 10^9/L$ , OR
  - b. Hgb  $< 100$  g/L have received  $\geq 2$  units PRBC in the 12 weeks prior to study entry, and be intolerant of or had inadequate response to ruxolitinib;
8. Subjects must have an Eastern Cooperative Oncology Group (ECOG) Performance Status of 0-2. ([APPENDIX F](#));
9. Life expectancy of at least twelve months;
10. At least four weeks must have elapsed between the last dose of any MF-directed drug treatments for myelofibrosis (including investigational therapies) and study enrollment;
11. Recovery to  $\leq$  Grade 1 or baseline of any toxicities due to prior systemic treatments, excluding alopecia;

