### **7.11.1 Bone Marrow Biopsy**

Bone marrow biopsy will be performed at screening, Cycle 4, Day 1, Cycle 7, Day 1, and Cycle 9, Day 29. Analysis will include confirmation of diagnosis and assessments of reticulin stain and trichrome stain. Slides will be sent to a central committee of hematopathologists who will be

blinded to subject, treatment, and collection time for centralized grading of fibrosis. A charter will be established for the central committee. Quantification of marrow fibrosis will be performed in a blinded fashion by computer assisted image analysis. Unstained slides will be collected for analysis of disease and mechanism related changes.

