2.2.2 Secondary Efficacy Endpoints

The secondary efficacy endpoints are as follows for:

Stage 1:

- Bone Marrow MF grade shifts relative to baseline over time
- Modified Myeloproliferative Neoplasm-Symptom Assessment Form Total Symptom Score (MPN-SAF TSS) changes from baseline over time

Stage 2:

- Bone Marrow improvement:
 - Bone marrow (BM) response rate (MF Grade) at each visit (reduction of 1 grade versus baseline)
 - Duration of BM response defined for responding subjects as time from first decrease from baseline of one grade to time of return to baseline levels. If no return to baseline levels or worse than baseline then duration will be censored at the last BM assessment.
- Hemoglobin improvement (number and percentage of subjects):
 - For red blood cell transfusion dependent subjects at baseline (at least 2 units every 4 weeks for 12 weeks prior to Cycle [C]1Day [D]1), improvement is defined as either:
 - 1) absence of any packed red blood cells (PRBC) transfusion during any consecutive 12 weeks interval with hemoglobin level of ≥80g/L

OR

- 2) at least a 50% reduction in PRBC transfusions for 12 consecutive weeks with hemoglobin level of ≥80g/L
- For red blood cell transfusion independent subjects improvement is defined as:
 - ≥10 g/L increase in hemoglobin level for 12 consecutive weeks without transfusions
- Platelet improvement (number and percentage of subjects)

- For transfusion dependent subjects at baseline, improvement is defined as either:
- 1) becoming transfusion independent for 12 consecutive weeks

OR

- 2) reduction in transfusions need ≥50% from baseline for 12 consecutive weeks
- For transfusion independent subjects with baseline platelet count below 100^9/L, improvement is defined as:
 - ≥50% increase in the number of platelet for 12 consecutive weeks or normalization of platelet count (above lower limit normal)
- Symptom improvement:

Percent of subjects with 50% reduction in MPN-SAF TSS from baseline over time(Tefferi 2013)

• Percent of subjects with complete response, partial response, clinical improvement, stable disease and progressive disease according to IWG-MRT criteria.

2.2.3 Exploratory Efficacy Endpoints

The exploratory efficacy endpoints are as follows for:

Stage 1:

- Bone marrow biopsy results for:
 - Myeloblasts (%), at each time point and change from baseline
 - Cellularity (%), at each time point and change from baseline
 - Collagen and reticulin grade shifts relative to baseline over time

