4.3 ANALYSIS OF TREATMENT GROUP COMPARABILITY

Descriptive summaries will be provided for all baseline characteristics. The summaries will be provided for both stages separately. Demographic and baseline variables that will be summarized by treatment group include at least:

- Stratification factors (Stage 2 only):
 - Baseline anemia (Hgb < 100 g/L and having received > 2 units PRBC in 12 weeks prior to study entry) alone
 - Baseline thrombocytopenia (platelet count < 50 x 10⁹ /L) alone
 - Baseline anemia associated with baseline thrombocytopenia
- Demographics for both Stages:
 - Gender
 - Age at consent (continuous and categorical)
 - Race
 - Ethnicity (if available)
 - Weight at baseline

Should country policy prohibit the collection of race and/or age information, subjects will appear in the missing category of summary tables.

- MF history for Stage 1:
 - Number of years since diagnosis
 - Bone marrow fibrosis grade at baseline
 - Spleen size below left costal margin at baseline
 - Type of MF (PMF, post-PV MF or post-ET MF)
 - Risk group with PMF (low, intermediate-1, intermediate-2, or high)
 - Red blood cell transfusion history 3 months prior to first dose
 - Number of subjects transfused (PRBC, Platelets, Fresh frozen plasma)
 - Number of subjects with baseline hemoglobin < 100 g/L at baseline
 - Number of subjects with platelets < 50 g/L and <25 g/L at baseline
 - Number of units of platelet and RBC transfusions
 - Number of subjects previously treated with ruxolitinib
- MF history for Stage 2:
 - Number of years since diagnosis
 - Bone marrow fibrosis grade at baseline
 - Spleen size measured by CT, positron emission tomography-CT (PET-CT) or MRI at baseline
 - Type of MF (PMF, post-PV MF or post-ET MF)
 - Risk group with MF (DIPSS low, intermediate-1, intermediate-2, or high)
 - Number of subjects with at least one transfusion in 12 weeks prior to baseline (RBC and platelet)
 - Number of subjects with baseline hemoglobin < 100 g/L at baseline
 - Number of subjects with platelets < 50 g/L and <25 g/L at baseline
 - Number of units of platelet and RBC transfusions
 - Number of subjects previously treated with ruxolitinib

In addition, for both stages, ruxolitnib history will be presented.

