- Myeloblasts and cellularity will be presented at baseline, Weeks 12 and 24 as well as change from baseline
- Collagen grade shifts relative to baseline at Weeks 12 and 24.

The modified MPN-SAF TSS will be presented descriptively at baseline and at the beginning of each cycle (Cycle 2 onward). In addition, the number of subjects with \geq 25% and \geq 50% reduction relative to baseline at the beginning of each cycle (Cycle 2 onward) will be presented.

Stage 2:

Duration of effect of the three doses on reduction in bone marrow fibrosis:

- To assess the duration of effect of the three doses on bone marrow improvement a
 Kaplan-Meier plot will be provided. Duration of BM improvement will be defined for
 responding subjects as time from first decrease from baseline of one grade to time of
 return to baseline levels. If no return to baseline levels then duration will be
 censored at the last BM assessment
- Effect and duration of effect of the three doses on disease related anemia, thrombocytopenia, and constitutional symptoms: For patients with improvement, the duration of improvement is defined as the number of weeks of improvement from the first12 weeks of improvement period.

IWG-MRT response will be summarized by treatment group at each visit by percent of subjects with complete response, partial response, clinical improvement, stable disease and progressive disease according to IWG-MRT criteria.

4.4.3 Exploratory Efficacy Endpoints

The exploratory endpoints will be summarized using tables, listings and graphs as appropriate.

4.4.4 Sensitivity Analyses

For Stage 2, a non-stratified analysis of BMRR will be computing as a sensitivity analysis.

4.4.5 **Subgroup Analyses**

Stage 1:

• Primary endpoint results will be presented by risks groups (intermediate-1, intermediate-2, or high risk subjects).

Stage 2:

- Primary endpoint results will be presented:
 - by risks groups (intermediate-1, intermediate-2, or high risk subjects)
 - for each strata separately (baseline anemia alone, baseline thrombocytopenia alone, baseline anemia and thrombocytopenia)
 - by transfusion status at baseline with transfusion dependency defined as: ≥ 2
 units PRBC every 4 weeks for 12 weeks prior to or after C1D1
 - by PTX-2 level at baseline classify by High/Low category (median as the cutoff)

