Not transfusion dependent	consecutive weeks without transfusions
Platelet improvement:	
Baseline Status	Categories of Platelet Improvement
Subjects who are transfusion dependent (≥ 2	Percent of subjects with:
platelet transfusions in any 12 weeks prior to	Platelet transfusion independence (no
or after C1D1), regardless of baseline platelet	transfusions for ≥ 12 consecutive weeks)
level	
	OR
Platelet transfusion = either 1 unit apheresed	
(single donor) platelets or 4-8 units pooled	50% reduction in platelets transfusions for
random donor platelets	≥ 12 consecutive weeks
Subjects with 25 < baseline platelets < 50 x	Percent of subjects with:
10^{9} /L	Doubling of baseline platelet count for ≥ 12
AND	consecutive weeks without platelet
Not platelet transfusion dependent	transfusions
	OR
	Platelet count $> 50 \times 10^9 / L \text{ for } \ge 12$
	consecutive weeks without platelet
	transfusions
Subjects with baseline platelet count $< 25 \text{ x}$	Percent of subjects with:
$10^{9}/L$	Doubling of baseline platelet count for ≥ 12
AND	consecutive weeks without platelet
Not platelet transfusion dependent	transfusions
	9.00
	OR
	Platelet count > 25 x 10^9 /L for ≥ 12
	consecutive weeks without platelet
	transfusions
Hematologic improvement:	,
	Catagories of Hamatalagia Impunyariant
Baseline Status Subjects with both Hemoglobin < 100 g/L	Categories of Hematologic Improvement Percent of subjects who have EITHER
and Platelets < 50 x 10 ⁹ /L	Hemoglobin improvement OR Platelet
and I fatelets > 50 x 10 /L	
	improvement as described above and no
	worsening of hemoglobin or platelets from baseline
Subjects with only Hemoglobin < 100 g/L	Percent of subjects who have Hemoglobin
Subjects with only Hemogroum > 100 g/L	improvement as described above
	AND
	Did not develop platelets < 50 x 10 ⁹ /L
	Did not develop plateiets > 30 x 10 /L

Subjects with only Platelets $< 50 \times 10^9/L$	Percent of subjects who have Platelet
	improvement as described above
	AND
	Did not develop Hemoglobin < 100 g/L or
	new transfusion dependence

- Symptom improvement:
 - Percent of subjects with 25% and 50% reduction in MPN-SAF Total Symptom Score from baseline at Week 36
 - o Mean change from baseline in EORTC QLQ-C30 at 36 weeks
- Duration of all improvement parameters listed above
- Percent of subjects with complete response, partial response, clinical improvement, stable disease, and progressive disease according to IWG-MRT criteria (Tefferi 2013, Appendix B)

Exploratory:

- Bone marrow

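### The Stage 2 BMRR subgroup labelled as baseline transfusion status (SAP 4.4.5) can be filled by on-treatment transfusions and does not match the pre-treatment definition in SAP 2.2.2

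*SAP*

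**What the plan says.** SAP 4.4.5 lists four Stage 2 presentations of the primary endpoint: by risk group, by randomisation stratum, by transfusion status and by baseline PTX-2 level. The third is introduced as "by transfusion status at baseline with transfusion dependency defined as" at least 2 "units PRBC every 4 weeks for 12 weeks prior to or after C1D1".

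SAP 2.2.2, for Stage 2 hemoglobin improvement, also speaks of red-cell dependence at baseline, but describes it as "at least 2 units every 4 weeks for 12 weeks prior to Cycle [C]1Day [D]1". The post-C1D1 alternative is gone.

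The wider wording comes from the hemoglobin improvement table in protocol 3.2, which is reprinted in SAP Appendix 3. SAP 4.4.5 kept it and SAP 2.2.2 did not. The SAP does not explain the difference.

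For platelets, SAP 2.2.2 says "For transfusion dependent subjects at baseline, improvement is defined as either" and then gives the improvement criteria without defining dependence. The only platelet threshold in the SAP is in Appendix 3: at least 2 "platelet transfusions in any 12 weeks prior to" or after C1D1.

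**The concern.** A baseline subgroup should be fixed before treatment starts. Under the rule in SAP 4.4.5, a subject who is not dependent before C1D1 can join the dependent subgroup through transfusions given while on the randomised dose. If dose affects transfusion need, membership is partly an outcome of treatment, and a comparison of doses within the subgroup loses the protection of randomisation.

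There is also a consistency problem. The same subject can be dependent in the BMRR subgroup table and independent in the hemoglobin improvement table of the same report, with both tables describing the status as baseline.

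**Working it through.** No figure in the plan depends on this definition, so there is none to reproduce. The check has three parts.

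**1. Definitions side by side**

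| Place | Used for | Described as | Red-cell window |
|---|---|---|---|
| Protocol 3.2 | Hemoglobin improvement | Baseline status | 12 weeks before or after C1D1 |
| SAP 2.2.2 | Hemoglobin improvement | At baseline | 12 weeks before C1D1 |
| SAP 4.4.5 | BMRR subgroup | At baseline | 12 weeks before or after C1D1 |

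The unit threshold is the same in all three. Only the window differs.

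**2. What the added window contains**

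I take the added window to be the 12 weeks that directly follow C1D1.

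- Dosing (protocol 6.3) is on Days 1, 3 and 5 of Cycle 1, then on Day 1 of Cycles 2 to 9: 3 + 8 = 11 infusions.
- Twelve weeks are 3 x 28 = 84 days, that is Cycles 1 to 3. They contain 3 + 2 = 5 of the 11 infusions.
- Dependency needs 2 units in each of three four-week periods: 2 x 3 = 6 units. The anemia entry route in protocol 5.1.1 asks for at least 2 "units PRBC in the 12 weeks prior to study entry, and be intolerant of or had inadequate response to ruxolitinib". A subject can therefore be eligible on 2 to 5 units without being dependent, and cross the line later.

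The last step shows only that crossing is possible. Eligibility counts back from study entry and dependency counts from C1D1. Screening can take up to four weeks, so the two 12-week windows need not coincide.

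**3. Effect of one reclassified subject (illustration)**

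Inputs: 84 / 3 = 28 subjects per arm; response rates of 46% and 5% (5% is the assumption for the 0.3 mg/kg arm), both from protocol 10.1; n = 4 to 14 dependent subjects per arm, which is my assumption and has no source in the documents.

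Adding one subject to a subgroup of size n with response rate p changes its rate by +(1 - p)/(n + 1) for a responder and by -p/(n + 1) for a non-responder.

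| p | n | Responder added | Non-responder added |
|---|---|---|---|
| 0.46 | 4 | 0.54/5 = +10.8 points | 0.46/5 = -9.2 points |
| 0.46 | 14 | 0.54/15 = +3.6 points | 0.46/15 = -3.1 points |
| 0.05 | 4 | 0.95/5 = +19.0 points | 0.05/5 = -1.0 points |
| 0.05 | 14 | 0.95/15 = +6.3 points | 0.05/15 = -0.3 points |

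The non-dependent subgroup loses the same subject, so its rate moves in the opposite direction. The table shows how sensitive a small subgroup is to one subject. It does not show that any subject is in fact moved.

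**The case against.** The best defence is that SAP 4.4.5 follows the protocol. Protocol 3.2 itself files the wider window under baseline status, so SAP 2.2.2 is the section that departs. This stands as an account of where the wording came from, and it means that the edit to 4.4.5 must be recorded as a departure too. It does not make transfusions after first dose a baseline characteristic, and it does not reconcile the two SAP sections.

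A second defence is that little depends on the table. It is one of four descriptive presentations, with no subgroup test, interaction test or decision rule. That is correct and limits the severity.

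Three stronger readings are tempting, but the documents do not support them:

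- *The classifying window overlaps the BMRR assessments.* Protocol 7.11.1 says: "Bone marrow biopsy will be performed at screening, Cycle 4, Day 1, Cycle 7, Day 1, and Cycle 9, Day 29". With C1D1 as Day 1, the window is Days 1 to 84 and Cycle 4 Day 1 is Day 85. The window ends just before the first scheduled post-baseline biopsy, and only the 3-day visit allowance could make them touch. What can be said is that the window lies on treatment and may depend on dose.
- *SAP 4.3 is a further conflicting definition.* Its entry reads "Number of subjects with at least one transfusion in 12 weeks prior to baseline (RBC and platelet". That counts subjects with any transfusion before baseline. It does not define dependency.
- *A known share of subjects is misclassified.* Any such share needs transfusion rates, and the documents give none.

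**Conclusion.** The inconsistency is certain from the text: two SAP sections define the same baseline red-cell status with different windows, and the one in 4.4.5 admits post-randomisation events. Followed as written, it produces a subgroup that cannot be read as a baseline subgroup and need not agree with the hemoglobin improvement analysis.

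The consequence is minor. The primary BMRR analysis, the comparison with the 10% threshold, the pairwise dose tests and the red-cell rule in SAP 2.2.2 are unaffected. The number of subjects reclassified and the direction of any net bias are unknown. The per-subject shifts rest on an assumed subgroup size and on the protocol's planning rates.

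The platelet point is secondary. The threshold exists in Appendix 3, but its post-C1D1 window conflicts with the baseline label in SAP 2.2.2. It does not touch the BMRR subgroup, which is based on red cells only.

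**What to change.** - In SAP 4.4.5, delete the words 'or after', so that red-cell dependency uses only the 12 weeks before C1D1, as in SAP 2.2.2.
- Document the pre-C1D1 window in both 2.2.2 and 4.4.5 as a departure from the wording of protocol 3.2.
- SAP section 1 shows that this SAP was written after the Stage 2 primary database lock and analysis, under an earlier Stage 2 SAP that is not among these documents. If that analysis used the wider rule, show its result beside the new one, labelled as a post-baseline classification.
- Wherever SAP 2.2.2 refers to platelet dependence at baseline, state the Appendix 3 threshold (at least 2 platelet transfusions) with the same pre-C1D1 window.

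The cost is a two-word deletion, one platelet definition and a note of the departure. No new data are needed: protocol 7.5 already records transfusions for three months before screening and from screening to first dose. The downside is a possibly smaller dependent subgroup and possible differences from earlier Stage 2 results, which the side-by-side display would make visible.

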## 1.4. Study Rationale

PTX-2 and PRM-151 have demonstrated the ability to reduce pre-existing fibrosis in multiple pre-clinical models in different fibrotic diseases, including TGF- $\beta$ 1 and bleomycin-induced lung fibrosis, unilateral ureteral obstruction (UUO) and ischemia reperfusion injury (IRI) induced renal fibrosis, and radiation induced oral mucositis. The pathogenesis of fibrosis in myelofibrosis is not well understood, but preliminary data suggests that, similar to other fibrotic diseases, insufficient production of PTX-2 may play a role. In idiopathic pulmonary fibrosis (IPF), for example, studies have shown that subjects with IPF have lower levels of PTX-2 than healthy volunteers, and lower levels of PTX-2 are associated with poorer lung function in IPF subjects (Murray, Chen et al.2011).

Until recently, the fibrosis in myelofibrosis was thought to be "reactive;" with overproduction of cytokines by malignant cells stimulating fibroblast-like cells derived from non-malignant mesenchymal stromal cells. This hypothesis has been weakened by the fact that ruxolitinib, which causes significant reduction of PMF-associated cytokine levels, does not appear to affect bone marrow fibrosis (Verstovsek, Kantarjian et al. 2010). Verstovsek *et al* (Verstovsek 2013, manuscript in preparation) have recently reported findings that suggest that bone marrow derived fibrocytes from subjects with myelofibrosis come from the malignant clone rather than from mesenchymal stromal cells (MSCs). Clonal neoplastic fibrocytes were identified in bone

marrows of subjects with PMF, and Jak2 mutations and chromosomal abnormalities present in the malignant clones in several subjects were present in the bone marrow derived fibrocytes but not in the MSCs. Furthermore, serum PTX-2 levels were significantly lower in subjects with PMF than healthy volunteers, and PTX-2 inhibited differentiation of monocytes from PMF bone marrows into fibrocytes *in vitro*. Data with PRM-151 in other fibrotic disease models combined with these findings in PMF subject bone marrows support investigation of PRM-151 in subjects with PMF.

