## **2.3 Exploratory Objectives**

The exploratory objectives of this study are:

- To measure changes in bone marrow fibrosis by quantitative image analysis and evaluate changes in bone marrow morphology in subjects receiving PRM-151
- To assess the effect of PRM-151 on other disease related parameters, including hematologic abnormalities and spleen size
- To assess the effect of PRM-151 on prognostic factors associated with increased mortality as measured by the DIPSS (Dynamic International Prognostic Scoring System)
- To evaluate the interaction between selected genetic mutations and cytogenetic abnormalities and response to PRM-151
- To explore potential biomarkers of PRM-151 activity in bone marrow samples
- To assess the effect of PRM-151 on bone marrow metabolism by PET imaging (at selected institutions)
- To evaluate the correlation of baseline PTX-2 levels with outcomes
- To evaluate the relationship between bone marrow fibrosis reduction and hematologic improvements in subjects treated with PRM-151
- To measure progression-free and overall survival in subjects receiving PRM-151

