  - Association of baseline mutational status of JAK2V617F, MPLW515, Calreticulin, ASXL1, EZH2, SRSF2, IDH1/2 with selected primary and secondary endpoints
  - Changes in allele burden of JAK2V617F at week 36. Changes in allele burden of MPLW515, Calreticulin, ASXL1, EZH2, SRSF2, IDH1/2 at week 36 will be measured as commercially available assays become available.
  - Association of baseline cytogenetic abnormalities and selected primary and secondary endpoints
- Association of baseline PTX-2 levels with selected primary and secondary endpoints
- Evaluation of potential biomarkers of PRM-151 activity in bone marrow biopsies taken at baseline, weeks 12, 24, and 36

- Measurement of progression-free and overall survival

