#### **10.6.1.3.4. Inferential analyses for secondary and exploratory efficacy endpoints:**

For all categorical or quantitative secondary efficacy endpoints, formal pairwise between arms comparisons will be computed. These comparisons will use a two-sided 0.05 level of significance, hence without any correction for multiplicity (See section 10.3.3). The results of these tests will have to be interpreted cautiously bearing in mind the issue of multiplicity and the increased risk of erroneously obtaining statistically significant results.

No between arms comparisons will be computed for the exploratory efficacy endpoints, only descriptive analyses will be computed.

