2.3 PHARMACOKINETIC ENDPOINTS

In Stage 1, the individual plasma concentration-time data following intravenous infusion of rhPTX-2 will be analyzed to obtain the following pharmacokinetic (PK) parameters, where applicable:

- C_{max} (maximum observed plasma concentration)
- t_{max} (time at which the maximum plasma concentration was observed)
- AUC_{0-last} (area under the plasma concentration-time curve from time 0 to time of last measurable plasma concentration)
- AUC_{0-∞} (area under the plasma concentration-time curve from 0-time extrapolated to infinity)
- t_{1/2} (apparent terminal elimination half-life)
- CL (clearance)
- Vd (volume of distribution)

The PK endpoint for Stage 2 subjects is the total PTX-2 level prior to drug administration at the pre-defined timepoints (see Appendix 5 and Appendix 6 Schedule of Assessment). Samples for rhPTX-2 PK analysis were not collected in Stage 2.

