4.6 BIOMARKER ANALYSES

All biomarker data will be presented in a dedicated report.

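### The SAP links baseline PTX-2 to marrow response only through a split at the sample median; a continuous model would serve the exploratory objective better

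*SAP*

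**What the plan says.** Protocol 2.3 lists as an exploratory objective "To evaluate the correlation of baseline PTX-2 levels with outcomes", and Protocol 3.3 lists the matching endpoint: "Association of baseline PTX-2 levels with selected primary and secondary endpoints". Neither names a method or a cutpoint. Protocol 1.4 gives the background: preliminary data suggest that too little PTX-2 may play a part in the disease, and "serum PTX-2 levels were significantly lower in subjects with PMF than healthy volunteers".

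The Stage 2 exploratory endpoint list in SAP 2.2.3 does not carry this endpoint; it appears only in the protocol synopsis reproduced in SAP Appendix 3. PTX-2 meets response in one bullet of SAP 4.4.5, which presents the primary endpoint "by PTX-2 level at baseline classify by High/Low category (median as the cutoff"). No reason is given for the median, and the bullet covers no secondary endpoint.

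The SAP treats PTX-2 as a pharmacokinetic measure: "The PK endpoint for Stage 2 subjects is the total PTX-2 level prior to drug administration". SAP 4.5 summarises it over time on its continuous scale but does not relate it to response. SAP 4.6 adds: "All biomarker data will be presented in a dedicated report". It does not say whether baseline PTX-2 against response belongs there.

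**The concern.** The protocol asks about the association between a continuous measurement and outcome. A two-row table at the median of whoever enrolled answers that weakly. It ignores variation within each half and treats subjects just either side of the cut as different. It also yields a cutpoint with no stated biological meaning that another trial could not reuse.

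At stake is how informative this exploratory estimate is. A real gradient could look like noise, particularly if the table is shown by dose, where each half holds only 12 to 14 subjects. The remedy is close to hand: PTX-2 is sampled pre-dose at Cycle 1 Day 1 (Protocol 8.2), and SAP 4.4.1 already specifies a stratum-adjusted logistic model for BMRR.

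**Working it through.** The documents give no figure for the PTX-2 analysis, so there is none to reproduce.

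**Inputs from Protocol 10.1.** 24 subjects per arm (72), with 84 enrolled (28 per arm). Assumed response rates are 5% (0.3 mg/kg), 46% (10 mg/kg) and at least 46% (3 mg/kg; 46% used here).

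**Assumptions not in the documents.** The distribution of PTX-2, the shape of its relation to response, and the effect size (odds ratios of 1.5, 2 and 2.5 per SD tried).

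**Step 1: information kept by a median split.** Relative efficiency is the squared correlation between X and the indicator B = I(X > median). For standard normal X, Cov(X, B) = 1/√(2π) and Var(B) = 1/4. The squared correlation is therefore (1/(2π))/(1/4) = 2/π = 0.637, and the loss is 1 − 0.637 = 36%. In equivalent sample size, 72 × 0.637 ≈ 46 and 84 × 0.637 ≈ 53.

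**Step 2: dependence on the distribution.** With the effect linear on the scale named, the loss is 25% (uniform), 42% (logistic), 50% (Laplace), 48% (lognormal, sigma 0.5), 52% (exponential) and 73% (lognormal, sigma 1).

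**Step 3: power at this trial's size.** 20,000 simulated trials per scenario, normal PTX-2, linear on the logit, rates 5/46/46%, score test stratified by arm (not by randomisation stratum), two-sided 0.05:

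| OR per SD | N=72 continuous | N=72 split | N=84 continuous | N=84 split |
|---|---|---|---|---|
| 1.5 | 0.28 | 0.20 | 0.32 | 0.22 |
| 2.0 | 0.63 | 0.45 | 0.70 | 0.51 |
| 2.5 | 0.83 | 0.65 | 0.89 | 0.72 |

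With no effect, all four rejection rates lay between 0.047 and 0.050, so the gain does not come from an inflated type I error. With a flat 30% rate in every arm instead, the figures at OR 2 are 0.69 against 0.50 (N=72) and 0.76 against 0.57 (N=84).

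**Step 4: the case that favours the split.** If the truth is a step exactly at the median (odds ratio 4 between halves), power is 0.47 continuous against 0.58 split at N=72, and 0.54 against 0.66 at N=84.

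**Step 5: the table by dose.** Each half has 24/2 = 12 to 28/2 = 14 subjects per arm. The 95% half-width around 46% is 1.96 × √(0.46 × 0.54/n), or 28 points at n = 12 and 26 at n = 14.

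**Step 6: what the data can bear.** Expected responders among 84 are 28 × (0.05 + 0.46 + 0.46) ≈ 27, of whom 28 × 0.05 = 1.4 are in the 0.3 mg/kg arm. The chance of none there is 0.95^28 = 24%. One main-effect term for PTX-2 is feasible; a treatment-by-PTX-2 interaction is not dependable.

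**The case against.** The best reply is that this is a subgroup display for an exploratory question. Protocol 10.6.1.3.4 says "No between arms comparisons will be computed for the exploratory efficacy endpoints, only descriptive analyses will be computed", and SAP 4.4.3 says "The exploratory endpoints will be summarized using tables, listings and graphs as appropriate". No test, significance level or decision rule is attached to PTX-2, so power is not a criterion the plan set itself. That stands: the power figures only express the information lost. It does not rule out the proposal, because an odds ratio with a confidence interval for PTX-2 estimates an association and is not a comparison between arms.

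A reader might infer that the SAP has cut the protocol's objective down to a median split. The documents do not establish that. SAP 4.6 sends biomarker data to a separate report that may or may not cover this endpoint. SAP 1 also refers to a detailed Stage 2 SAP (version 2.0, 5 March 2018), signed before the primary database lock, which is not among the documents reviewed.

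A reader might also infer that a weak table could lead PTX-2 to be abandoned wrongly as a selection marker. No such rule appears in either document.

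Two technical objections also stand. The 36% is conditional (Steps 2 and 4). And an odds ratio per sample SD would be tied to this sample much as the median is, which is why the fix uses a fixed unit.

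**Conclusion.** The point holds as a minor improvement. Within this SAP, the median split is the only link between baseline PTX-2 and marrow response, and it is a weak answer to a question about correlation or association. The loss is about 36% if PTX-2 is roughly normal on some scale and acts linearly on the logit. At an assumed odds ratio of 2 per SD that costs about 18 to 19 percentage points of power. A flat statement that a third of the information is lost would go too far: the loss ran from 25% to 73% over the distributions tried, and a step at the median would favour the split. Nothing in the documents supports a step there, but nothing excludes it. The primary and secondary conclusions do not depend on this analysis.

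**What to change.** In SAP 4.4.5, add an exploratory logistic model for BMRR with log baseline PTX-2 (Cycle 1 Day 1, pre-dose) as a continuous covariate, adjusted for treatment and randomisation stratum. Use a penalised (Firth) fit if the 0.3 mg/kg arm has few or no responders. Report the odds ratio per log unit or per doubling with its 95% CI, as an estimate without a decision rule. Keep the median-split table as a display, and omit a treatment-by-PTX-2 interaction. Add a sentence saying whether the dedicated biomarker report covers this endpoint and which secondary endpoints are meant.

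The cost is one extra model on data already collected. Because this SAP was written after the Stage 2 primary database lock, the model should be labelled post hoc for the main-stage data.
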